2.4.2 Prior, concomitant and post therapies

Prior and concomitant medications will be summarized separately by cohort.

Medications will be classified as prior or concomitant as follows:

- Prior medications are defined as drugs taken and stopped prior to the Week 0 visit.
- Concomitant medications are defined as drugs taken at least once between Week 0 visit and the date of study completion (including those which were started prior to the Week 0 visit and continued into the Investigational Period).

Medications will be categorized into one (and only one) of above classes based on recorded or imputed start and end dates.

Medications will be presented in alphabetical order, by Anatomical Therapeutic Classification (ATC) codes and grouped by anatomical main group. Tables will show the overall number and percentage of participants receiving at least one treatment of a particular ATC code and at least one treatment in a particular anatomical main group.

2.5 Analysis of the primary objective

The primary objective of this study is to characterize those achieving seroprotection after receiving the 2020-2021 inactivated influenza vaccine in participants in all three cohorts. This will be achieved by estimating the seroprotection response rate.

A seroprotection responder is a participant achieving seroprotection as defined by a post-vaccination hemagluttination inhibition (HI) titer \geq 40.

The seroprotection response rate is defined as the proportion of participants with seroprotection.

2.5.1 Primary endpoint

The primary endpoint variable is achieving seroprotection as defined by a post vaccination HI titer \geq 40 (Yes/No) at Week 4.

The primary estimand is described by the following attributes:

- Treatment: 2020-2021 inactivated influenza vaccine in participants treated with ofatumumab 20 mg (Cohort 1), ofatumumab as commercially prescribed (Cohort 2) or iDMT as commercially prescribed (Cohort 3).
- Population: Relapsing MS participants subdivided into three cohorts as defined in Section 1.1
- Variable: Achieving seroprotection as defined by a post-vaccination HI titer ≥40 (Yes/No)
- Other intercurrent events: None
- Population-level summary: Proportion of participants who achieve seroprotection at Week 4

2.5.2 Statistical hypothesis, model, and method of analysis

The number and percentage of responders will be presented. A 95% confidence interval for the proportion of responders will be calculated using an exact method.

2.5.3 Handling of missing values/censoring/discontinuations

Non-responder imputation (NRI) for missing data will be applied. NRI is a conservative imputation method for dichotomous variables. NRI assumes that a participant is a treatment

failure if they discontinue the study prematurely. Hence, for missing data the primary variable outcome will be imputed to "No". Please refer to Appendix Section 5.1.3.3.

2.5.4 Supportive analyses

No supportive analyses are planned.

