12.4.4 Handling of missing values not related to intercurrent event

Non-responder imputation approach will be applied to missing postvaccination antibody titer.

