12.4.6 Supplementary analysis

12.4.7 Similar analyses will be performed by using observed data. Supportive analyses

Not applicable.

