12.5 Analysis of secondary endpoint(s)/estimand(s)

The secondary endpoint is achieving seroconversion defined as meeting one of the following two criteria:

- ≥ 4-fold increase in HI titers after vaccination (in participants with prevaccination HI titers ≥10) (yes/no) or
- postvaccination HI titers ≥40 (in participants with prevaccination HI titers < 10) (yes/no)

Proportion of participants achieved seroconversion at Week 4 will be estimated and the corresponding 95% confidence interval will be calculated using exact method.

Both non-responder imputation and observed case approaches will be applied in the analyses of seroconversion.

To assess the change in HI titers, geometric means will be calculated for pre- and post-vaccination HI titers.

To meet European Medicines Agency guidelines for protection for the Cohort, at least one of the following criteria has to be met:

- 1. Seroprotection rate is better than 70%;
- 2. Seroconversion rate is higher than 40%;
- 3. Ratio of geometric mean of post- to pre-vaccination HI titers ≥ 2.5 .

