DMS Document Management System EMA European Medicines Agency

EOS End of Study
FAS Full Analysis Set

GPS Global Statistical and Programming Environment

HI Hemagluttination Inhibition

IA Interim Analyses
MS Multiple Sclerosis

MedDRA Medical Dictionary for Drug Regulatory Affairs

NRI Non-responder Imputation

PK Pharmacokinetics

PRO Patient-reported Outcomes

PT Preferred Term

QIV Quadrivalent inactivated influenza vaccine

RAP Reporting & Analysis Process
RMS Relapsing Multiple Sclerosis
SAE Serious Adverse Event
SAF Safety Analysis Set
SAP Statistical Analysis Plan
SAS Statistical Analysis System

sc Subcutaneous

SOC System Organ Class

TEAE Treatment Emergent Adverse Events

TFLs Tables, Figures, Listings

iDMT Injectable Disease Modifying Therapy

1 Introduction

The purpose of this Statistical Analysis Plan (SAP) is to describe the statistical methods planned in Section 12 of the Clinical Study Protocol (CSP) version 00 (release date 10 November 2020) for the clinical trial COMB157GUS12 and any additional analyses, specifications or deviations from this planned protocol before clinical database lock (CDBL).

This SAP will be used to draft the Clinical Study Report (CSR) Section 9.7: Statistical methods and IA plans.

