2.7.3 Handling of missing values/censoring/discontinuations

Both NRI for missing data and observed data approaches will be applied. Result based on NRI will be used to meet the secondary endpoint. Other observed data approaches will be applied as sensitivity analyses.

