2.14 Interim analysis

For the purpose of earlier dissemination of results, an interim analysis will be performed after:

- all enrolled participants have completed the Investigational Period or discontinued the Investigational Period prematurely OR
- On/around March 29, 2021, whichever comes first.

Since there will be no hypothesis testing involved, statistical adjustment for the interim analysis will not be made at the stage of final analyses.

3 Sample size calculation

Sample size calculations were based on the proportion of participants who responded to influenza vaccination.

The sample size of 20 participants per arm is selected based on budget and need for early availability of results. The sample size of 20 subjects will provide estimates with margin of error (half-width of a 95% confidence interval) of 20.1%, 19%, and 17.5% corresponding to response rates of 70%, 75%, and 80%, respectively. Adjusting for 10% drop-out, 22 subjects will be enrolled in each arm.

4 Change to protocol specified analyses

There are no changes to protocol specified analyses.

5 Appendix

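### The SAP omits the protocol's observed-data analysis of seroprotection while declaring no change, so the primary rate would be tabulated under non-responder imputation alone

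*SAP*

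**What the plan says.** **Protocol, primary endpoint.** Section 12.4.4 sets the main rule: "Non-responder imputation approach will be applied to missing postvaccination antibody titer". The next relevant sentence is "Similar analyses will be performed by using observed data". It is printed inside the 12.4.7 heading, and the table of contents shows the same run-together line. Section 12.4.6 (Supplementary analysis) has no other content, and 12.4.7 (Supportive analyses) has its own entry, which is not applicable. The sentence therefore reads as the body of 12.4.6.

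**SAP, primary endpoint.** Section 2.5.3: "Non-responder imputation (NRI) for missing data will be applied". Section 2.5.4: "No supportive analyses are planned". Appendix 5.1.3.3 repeats the NRI rule, and section 2.13 plans nothing further. No SAP section gives seroprotection on observed data.

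**SAP, secondary endpoint.** Section 2.7.3, on seroconversion: "Both NRI for missing data and observed data approaches will be applied". NRI leads and the observed-data result is a sensitivity analysis.

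**SAP, declared changes.** Section 4: "There are no changes to protocol specified analyses". The SAP's introduction ties it to protocol "version 00 (release date 10 November 2020"), whereas the protocol under review is amended version 03.

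**The concern.** Set against the current protocol, the statement in SAP section 4 does not hold, because a protocol-specified analysis of the primary endpoint has no counterpart in the SAP. The SAP feeds the methods section of the study report, so the analysis could disappear without anyone having decided to remove it. The primary endpoint would also get a thinner treatment of missing data than the secondary one.

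The study tests no hypothesis, so the estimated rate and its interval are the result, and the handling of missing titers acts directly on them. SAP 2.5.3 supports NRI by treating early discontinuation as treatment failure. Here, however, the treatment of interest is a single vaccination that everyone in the SAP's analysis set has already received. A missed Week 4 draw is not in itself vaccine failure, so the NRI rate combines response with attendance. An observed-data rate beside it, with the number missing, lets a reader see how much of the figure is due to each.

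**Working it through.** **Inputs.** Evaluable participants per arm 20, drop-out 10%, enrolled per arm 22, and assumed response rates of 70%, 75% and 80% (Protocol 12.8.1, SAP section 3). Seroprotection criterion above 70% (Protocol 12.5, SAP 2.7). Analysis set: vaccinated participants (SAP 2.2). Exact 95% intervals (Protocol 12.4.2, SAP 2.5.2).

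**1. The plan's own figures.** Half-width = 1.96 × √(p(1−p)/20):
- p = 0.70: 20.08%
- p = 0.75: 18.98%
- p = 0.80: 17.53%

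These match the stated 20.1%, 19% and 17.5%. Enrolment: 20 × 1.1 = 22, as stated.

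**2. Expected rate under NRI.** If a fraction d of the analysis set lacks a Week 4 titer and missingness is unrelated to response (assumption), the expected NRI rate is p × (1 − d). With d = 0.10, true rates of 70%, 75% and 80% become 63%, 67.5% and 72%. For a true 75%:

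| Missing titers | Expected NRI rate |
|---|---|
| 0% | 75.0% |
| 5% | 71.25% |
| 6.7% | 70.0% |
| 10% | 67.5% |
| 15% | 63.75% |

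Break-even: 1 − 0.70/0.75 = 6.7%. In a cohort of 22, one missing titer (4.5%) gives 0.75 × 21/22 = 71.6%, and two (9.1%) give 0.75 × 20/22 = 68.2%. A full cohort therefore crosses the line, in expectation, at the second missing titer.

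**3. Worked case: 22 vaccinated, 20 titers, 15 responders.**
- Observed data: 15/20 = 75.0%, exact 95% CI 50.9 to 91.3%.
- NRI: 15/22 = 68.2%, exact 95% CI 45.1 to 86.1%.

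**4. Chance that the point estimate exceeds 70% at a true 75%, with exactly 2 of 22 missing.**
- Observed data needs at least 15 of 20 (14/20 is exactly 70%): probability 0.617.
- NRI needs at least 16 responders (15/22 = 68.2%, 16/22 = 72.7%) among the 20 observed: probability 0.415.

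If each of the 22 titers is missing independently with probability 10%, the chance that the observed rate exceeds 70% while the NRI rate does not is 0.29.

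**5. Protocol against SAP, analysis by analysis.**

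| Analysis | Protocol | SAP |
|---|---|---|
| Seroprotection, NRI | 12.4.4 | 2.5.3 |
| Seroprotection, observed data | 12.4.6 | none |
| Seroprotection, supportive | 12.4.7: not applicable | 2.5.4: none |
| Seroconversion, NRI and observed data | 12.5 | 2.7.3 |

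The only mismatch is in the second row.

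**The case against.** **SAP 2.5.4 might be read as cancelling the protocol's analysis.** The documents do not support that. SAP 2.5.4 has the same title as Protocol 12.4.7, and both plan nothing. The observed-data analysis sits under a different protocol heading that the SAP does not reproduce. One could even argue that section 4 leaves the protocol's analysis in force. This objection stands as to wording: the fault is an omission. It does not remove the gap, since a programmer working from the SAP would find nothing to produce.

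**The SAP was written for protocol version 00.** That text is not available, so section 4 may have been true when written. The protocol's summaries of Amendments 1 to 3 mention no change to missing-data analyses, but summaries need not be complete. The origin of the gap stays open. Aligning the SAP with the current protocol would still have to include this item.

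**A reader might infer that nothing would reveal the effect of missing titers.** That goes too far. SAP 2.1 lists all collected and derived data, SAP 2.3.1 lists discontinuations with the primary reason, the responder count is tabulated, and seroconversion is reported both ways. The observed rate could be rebuilt. What is missing is a planned table with an interval.

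**A reader might infer that a cohort fails if NRI takes it below 70%.** It does not. "Seroprotection rate is better than 70" per cent is one of three criteria, any one of which suffices, and nothing is tested. The two intervals in the worked case overlap heavily and both contain 70%. Even on observed data, a true 75% does not exceed 70% in about 38% of cases (1 − 0.617).

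**Ten per cent drop-out need not mean 10% missing titers.** This stands. Anyone lost before vaccination is outside the SAP's analysis set, and early discontinuers are asked back within 7 days for an end-of-study visit at which the titer is scheduled. Some of them will therefore have a value.

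**A reader might infer a distorted comparison with the iDMT cohort.** That would require missingness to differ between cohorts. The documents give no figures on this and plan no formal comparison, so the point does not rest on it.

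**Conclusion.** The protocol plans seroprotection on observed data alongside NRI. The SAP omits it for the primary endpoint, keeps the equivalent for seroconversion, and says that no protocol-specified analysis has changed. Against the current protocol that statement is incorrect and should be put right.

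The possible effect on the reported rate is moderate and conditional. A true 75% has an expected NRI rate of 67.5% if the full planned 10% becomes missing Week 4 titers among vaccinated participants and missingness is unrelated to response. Below 6.7% missing, the expected rate stays above 70%. NRI itself is not at fault: protocol and SAP agree on it as the primary rule, and the SAP describes it as conservative. The documents do not support a claim that the SAP deliberately cancels the analysis, that the observed rate would be unrecoverable, or that a cohort's overall conclusion turns on this one criterion.

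**What to change.** Add to SAP 2.5, as the protocol's supplementary analysis: the number and percentage of seroprotection responders with an exact 95% CI among participants with an observed Week 4 titer, by cohort, together with the number of missing titers. Keep NRI as the primary analysis.

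If the sponsor means to drop the observed-data analysis, say so and justify it in SAP section 4, and amend Protocol 12.4.6 to match.

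In the protocol, separate the 12.4.6 text from the 12.4.7 heading so that it is clear which section plans the analysis.

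The cost is one SAP paragraph and one extra table, using programming already needed for seroconversion. No additional data are collected.

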2.6 Analysis of the key secondary objective

There is not key secondary objective for this study.

2.7 Analysis of secondary objective(s)

The secondary objective of this study is to characterize those achieving seroconversion after receiving the 2020-2021 inactivated influenza vaccine in participants in all three cohorts where seroconversion is defined as:

- a ≥4-fold increase in HI titers after vaccination (in participants with pre vaccination HI titers ≥10) **OR**
- post vaccination HI titers \geq 40 (in participants with pre vaccination HI titers \leq 10)

The seroconversion response rate is defined as the proportion of participants with seroconversion.

To meet European Medicines Agency (EMA) guidelines for cohort protection, at least one of the following criteria has to be met:

- Seroprotection rate is better than 70%;
- Seroconversion rate is higher than 40%;
- Mean geometric increase of post- to pre-vaccination HI titers ≥ 2.5 .

2.7.1 Secondary endpoints

The secondary endpoint variable is achieving seroconversion as defined in Section 2.7 above (Yes/No) at Week 4.

2.7.2 Statistical hypothesis, model, and method of analysis

The number and percentage of responders will be presented. A 95% confidence interval for the proportion of responders will be calculated using an exact method. To assess the change in HI titers, geometric means will be calculated and summarized for pre- and post-vaccination HI titers.

2.7.3 Handling of missing values/censoring/discontinuations

Both NRI for missing data and observed data approaches will be applied. Result based on NRI will be used to meet the secondary endpoint. Other observed data approaches will be applied as sensitivity analyses.

2.8 Safety analyses

2.8.1 Adverse events (AEs)

An adverse event (AE) is any untoward medical occurrence (i.e., any unfavorable and unintended sign [including abnormal laboratory findings], symptom or disease) in a participant or clinical investigation of a participant after providing written informed consent for participation in the study. That means that a participant can report AEs before having started study medication. For reporting purposes, the main focus will be on any adverse event which started on or after the Week 0 visit.

The number (and percentage) of participants with AEs will be summarized by cohort in the following ways:

- by primary SOC and PT
- by primary SOC, PT and maximum severity
- by Standardized MedDRA Query (SMQ) and PT

Separate summaries will be provided for:

- serious adverse events (SAEs)
- AEs leading study discontinuation

Separate summaries will be presented for data collected during the Extension Period.

The MedDRA version used for reporting the study will be described in a footnote. If a particular Missing CTCAE grade will not be imputed. If a participant reported more than one AE with the same PT, the AE with the greatest severity will be presented. A participant with multiple AEs within a primary SOC is only counted once towards the total of the primary SOC.

All AEs will be listed by cohort.

